If necessary, the primary outcome distribution will be log transformed to satisfy assumptions. For secondary outcomes, the generalized linear model allows the specification of an array of distributions (e.g., normal, binomial, gamma) with corresponding link functions (e.g., log).

27e. Planned sensitivity analyses

Three sensitivity analyses will be performed to evaluate the robustness of the trajectory analysis to the primary and secondary analyses. These are to include multiple imputation for missing data, to include monthly through 6 months and the 12-month daily diary data and to include a change point rather than log of time model, as previously described [2]. Two other sensitivity analyses will be

performed to evaluate the robustness of other causes of variability in trajectory in the primary and secondary analyses: race and surgeon.

27f. *Planned subgroup analyses*

No subgroup analyses are planned.

28. *Missing data – reporting and assumptions/statistical methods to handle missing data*

Multiple imputation will be used to account for embedded missing data in daily diary entries. The autocorrelation of each time-series for each individual along with baseline predictors will be used in conjunction with the MICE algorithm to estimate $m = 20$ imputations. These imputations will then be re-analyzed using the primary model with Rubin's rules used to pool the estimates of model parameters.

29. *Details of any additional statistical analyses required e.g., complier-average causal effect analysis.*

None

30. *Harms*

The number (and percentage) of patients experiencing each AE/SAE will be presented for each treatment arm categorized by severity. For each patient, only the maximum severity experienced of each type of AE will be displayed. The number (and percentage) of occurrences of each AE/SAE will also be presented for each treatment arm. No formal statistical testing will be undertaken

31. *Statistical Software*

The analysis will be carried out using R version 4.1.2

32. *References*

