There were no planned interim analyses. An interim analysis was performed on Feb 8, 2019 after 49 subjects had completed the 2 month daily diary portion of the study. This was performed by the study statistician for the purpose of an NIH grant submission, with the study team remaining blinded to allocation assignments. Only descriptive statistics were performed and there was a decision prior to the analysis that early stopping would not be allowed based on the results.

13b. *Any planned adjustment of the significance level due to interim analysis*

None.

13c. *Details of guidelines for stopping a trial early*

There was no plan to stop the trial early aside from recommendations based on unanticipated serious adverse events by the DSMB.

14. *Timing of final analysis*

Final analysis of the oxytocin vs saline comparison will take place when all patients have completed the 12 month follow-up and data for the primary endpoint have been cleaned (anticipated January 2022). The first main report/publication of the primary endpoint will be prepared for submission, anticipated by May, 2022.

15. *Timing of outcome assessments*

The schedule of study procedures is provided in the protocol and summarized in the table below.

Phase	Ortho Clinic	V1 (COMPLETED 2-4 WEEKS PRIOR TO SURGERY)	14 DAYS Pre op- 1 day pre op	DOS	POD 1	POD 2- POD 56	Post op Week 1-8	Post op V2 (8-10 weeks)	Monthly follow up 3 mos	Monthly follow up 4 mos	Monthly follow up 5 mos	Monthly follow up 6 mos	Monthly follow up 12 mos
Obtain/Confirm Informed Consent	X	X		X									
Obtain Medical History	X	X											
Urine Pregnancy Test if applicable				X									
Questionnaires		X						X					
Iowa Gambling		X						X					
Card Sorting		X						X					
Daily Diary			X	X	X	X							
Weekly Diary (WHODAS)							X						
Step tracker			X		X	X							
Verbal Pain				X	X								
Monthly Diary									X	X	X	X	X

Section 4: Statistical Principles

16. *Level of statistical significance*

All applicable statistical tests will be 2-sided and will be performed using a 5% significance level.

17. *Adjusting for multiplicity*

The primary analysis involves a single model-based inference that will be interpreted at the 5% threshold of statistical significance. Multiple secondary outcomes will be evaluated and each will be interpreted at the 5% level of significance with no adjustments made for multiplicity.

18. *Confidence intervals*

All confidence intervals presented will be 95% and two-sided.

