Questionnaire and cognitive game data will be assessed at baseline and follow-up. Validated scoring systems from the individual items will be used to score each questionnaire or measure. For the purpose of the primary analysis publication, summary scores with measure of central tendency and variance will be provided for oxytocin and saline groups as mentioned in Item 25b.

27a. Analysis methods to be used and

27b. Adjustments for covariates

Primary analysis:

To examine how participants recover over the repeated measurement occasions, we will employ hierarchical linear modeling (HLM) [1]. The application of HLM to individual change data is well suited for the expected changes that occur after surgical injury. HLM is a polynomial regression with random effects where interaction terms are used to examine impacts on the change parameters (e.g., treatment group x intercept; treatment group x slope). Because of the nature of the expected change, the trajectories will be modeled using parameters consisting of an intercept and the slope estimated using the natural log of time (change in recovery). The intercept is coded to represent the initial level (first day after hospital discharge) of the outcome variable. The slope estimates the change over ln of time and represents the increase or decrease in the variable. Through the use of fixed and random effects, we will then be able to examine the influences on the changes in pain. In this way, we test efficacy of the test intervention, intrathecal oxytocin.

To examine the proposed hypothesis, we have *a priori* defined key fixed effects that will be included in the primary model, based on previous literature regarding their influence on recovery after surgery. This adjusted analysis is the primary analysis. Each of these predictors is described below:

Oxytocin: Randomized treatment assignment of either oxytocin or placebo will be a fundamental predictor of trajectory.

Patient characteristics: To adjust the associations for individual characteristics, age, sex, number of painful conditions beyond the operated hip, ongoing use of opioids at the time of recruitment, and PROMIS depression score will be entered into the model.

Preoperative study data: Degree of daily pain and its variance during the two weeks prior to surgery as assessed by daily diaries will be entered into the model.

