These individual predictors sets will then be used to test the primary hypothesis that oxytocin alters time course of recovery after TKA. The primary statistical inference will be a likelihood ratio comparing two models estimated with and without oxytocin group assignment. Thus, the pain trajectory model comparing medication assignment (oxytocin versus placebo) adjusted for the covariates of characteristics and preoperative study data will be compared to a similar model without medication assignment using a Chi-squared test. This approach allows a single direct test of the primary hypothesis and will be interpreted using a two-tailed hypothesis test using $p < 0.05$. A statistically significant difference will be interpreted as evidence to support the primary hypothesis that pain trajectory differs between oxytocin and saline treatment.

Secondary analyses: Trajectories for daily activity, as measured via actigraphy, disability, as measured by daily diaries and weekly WHODAS 2.0 scores, and opioid self-administration, as measured by daily diaries, will be analyzed using a similar approach to that of the primary outcome, with one exception. For the activity analysis, preoperative data covariate included will not be pain, but rather degree of daily actigraphy activity and its variance during the two weeks prior to surgery as assessed by daily diaries. For disability analysis, preoperative data covariate included will not be pain, but rather degree of daily disability and its variance during the two weeks prior to surgery as assessed by daily diaries and baseline WHODAS 2.0 score. As noted, with the exception of the PROMIS depression score, other questionnaire and cognitive game scores will be described for the two groups but not analyzed or entered as covariates for the purpose of the primary analysis and publication. Changes in questionnaire data will be evaluated using the generalized linear model regressing follow-up score on baseline score and medication group assignment.

27c. Methods to be used for assumptions to be checked for statistical methods for primary and secondary analyses

The assumptions underlying parametric modeling will be evaluated using regression diagnostic procedures and histograms of residuals.

27d. Alternative methods to be used if distributional assumptions do not hold for primary and secondary analyses

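### The primary likelihood-ratio test uses a plain chi-squared reference; with about 120 patients and seven covariates its size is probably about 6%, not 5%, depending on model details the SAP leaves open

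*SAP*

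**What the plan says.** SAP 27a/27b describes a hierarchical linear model for daily worst pain, with an intercept and a slope in ln(time). It mentions interaction terms with arm ("e.g., treatment group x intercept; treatment group x slope"). The covariate-adjusted model is declared primary. Its covariates are all measured per patient: "age, sex, number of painful conditions beyond the operated hip, ongoing use of opioids at the time of recruitment, and PROMIS depression score", plus "Degree of daily pain and its variance during the two weeks prior to surgery". That is five and two, seven in all.

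The test is then defined: "The primary statistical inference will be a likelihood ratio comparing two models estimated with and without oxytocin group assignment". The model with arm "adjusted for the covariates of characteristics and preoperative study data will be compared to a similar model without medication assignment using a Chi-squared test".

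The error rate is set in SAP 16 ("All applicable statistical tests will be 2-sided and will be performed using a 5% significance level") and SAP 17 ("The primary analysis involves a single model-based inference that will be interpreted at the 5% threshold of statistical significance"). SAP 11 plans 120 patients, 60 per arm.

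The SAP gives no degrees of freedom for the test, no estimation method, no list of random effects, and no rule on whether covariates act on the slope. It names no small-sample reference distribution. The sensitivity analyses in SAP 27e (multiple imputation, longer follow-up, change point, race, surgeon) do not examine the reference distribution.

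**The concern.** Each patient receives one arm, so the arm effect on the trajectory is a between-patient contrast. Once each patient has their own intercept and slope, the sample that matters is the number of patients.

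A likelihood ratio between models with different fixed effects requires ML, because REML likelihoods are not comparable across them. ML divides by the number of patients and makes no allowance for the fixed effects estimated. The between-patient variance is then understated, the statistic is too large, and a chi-squared cut-off rejects too often under the null.

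This is the trial's only confirmatory test, and the same approach is carried over to the secondary trajectories. The direction of the error is known before unblinding, and no other part of the SAP corrects it.

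**Working it through.** **Inputs from the documents.** n = 120 (SAP 11); k = 7 patient-level covariates (SAP 27b); two-sided 5% (SAP 16, 17); likelihood ratio against chi-squared (SAP 27b); permuted blocks of 4 to 8 (SAP 10).

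**Assumptions, because the SAP is silent.** ML fits; a correctly specified random intercept and random ln(time) slope per patient; complete diaries on a common schedule. The arm terms removed are taken to be arm and arm x ln(time), so 2 df.

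**1. The plan's figure.** The chi-squared 95% points are 3.841 (1 df) and 5.991 (2 df), each with tail area 0.0500. The stated 5% is correct as a large-sample value.

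**2. Joint 2-df test, covariates on intercept and slope.** For balanced data the statistic equals n x ln(1/Wilks lambda) on the per-patient coefficients, with n - 2 - k error degrees of freedom. So

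size = P[F(2, n-3-k) > (exp(5.991/n) - 1)(n-3-k)/2].

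With n = 120 and k = 7, the threshold is (exp(5.991/120) - 1) x 110/2 = 2.816, and P[F(2,110) > 2.816] = 0.0642.

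For 2 numerator df this simplifies to 0.05^((n-3-k)/n):

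| n | k | exponent | size |
|---|---|---|---|
| 120 | 7 | 110/120 | 6.42% |
| 108 | 7 | 98/108 | 6.60% |
| 100 | 7 | 90/100 | 6.75% |
| 120 | 0 | 117/120 | 5.39% |

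The last row shows that about 0.4 point of the excess is present with no covariates.

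On this reading, at n = 120, the correct cut-off is 5.991 x 120/110 = 6.54. That corresponds to a nominal p of 0.05^(120/110) = 0.038. A nominal p of 0.050 corresponds to 0.064.

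**3. Joint 2-df test, covariates on the level only.** This was simulated. Two runs, of 30,000 and 20,000 null trials, gave 5.9% and 6.0% (Monte Carlo standard errors about 0.14 and 0.17 point). The 20,000-trial run used 56 days, blocks of 4, 6 and 8, and assumed random-effect SDs of 2.0 and 0.6 with residual SD 1.5. It gave 6.5% for the case in step 2 and 5.5% with no covariates, in line with the exact 6.4% and 5.4%.

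**4. A 1-df slope test.** With covariates on both parts, size = P[F(1, n-2-k) > (n-2-k)(exp(3.841/n) - 1)] = P[F(1,111) > 3.611] = 6.0% (simulated 5.9%). With covariates on the level only, the simulated size is 5.1%.

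**5. Dependence on the random slope.** If only a random intercept were fitted, 2,000 simulated trials per setting (assumed intercept SD 2, residual SD 1.5) gave joint-test sizes of 5.0-5.4% with no true slope variation. Size was about 11-14% with a true ln-slope SD of 0.2, and about 41-42% with 0.6.

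**6. Power at the corrected cut-off.** At an alternative where the F(2,110) test has 80% power (noncentrality 9.90), the uncorrected test rejects 83% of the time.

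**The case against.** The strongest objection is that 6% is conditional. The SAP fixes none of the four details on which it depends, and one admissible version is nearly nominal. The protocol describes its primary analysis as the slope, and a 1-df slope test with level-only covariates has size about 5.1%. This stands as a limit on the claim. However, SAP 27b removes arm as a whole from a model in which arm acts on intercept and slope, and that is most naturally a joint 2-df test.

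A reader might infer that the true error rate is 6.4% outright, so that p = 0.050 is really 0.064 and the cut-off is really 6.54. The documents do not support that. Those figures need all seven covariates to act on the ln(time) slope, and SAP 27b lists no covariate-by-time terms. Nor are the covariates the sole cause: on the level-only reading they add only about 0.5 to 0.6 point to the 5.4% found without them.

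A reader might also infer, from the silence on random effects, that the plan omits the random slope and has error rates of 11% or more. The documents do not say so. The protocol's analytical plan speaks of a trajectory unique to each person, which points to a random slope. The large figures also rest on assumed SDs.

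Finally, a chi-squared likelihood-ratio test with about 120 patients is ordinary practice, and the excess is small. That is fair and it limits the severity. The secondary trajectories add little weight, since SAP 17 already tests them without multiplicity control.

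**Conclusion.** The concern holds in a modest form. Under ML with a random intercept and ln(time) slope, the joint 2-df test has true size of about 5.9-6.0% (covariates on the level only) to 6.4% (covariates on intercept and slope), against the stated 5%. A 1-df slope test would range from about 5.1% to 6.0%.

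The excess is therefore 0.1 to 1.4 points at n = 120, depending on choices the SAP has not recorded, and somewhat more if fewer patients are analysed. At worst, at n = 120, it reverses the conclusion for a nominal p between about 0.038 and 0.050. The exact figures assume balanced, complete diaries. Severity is minor to moderate: small in size, anticonservative in direction, and cheap to remove.

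**What to change.** In SAP 27b:

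1. State a random intercept and a random ln(time) slope per patient.
2. State the arm terms tested: arm and arm x ln(time), 2 df. State also whether the covariates act on the level only or on the slope too.
3. Replace the chi-squared reference with a Kenward-Roger F test of those arm terms from the REML fit, or with a re-randomisation test that follows the permuted-block scheme.
4. Use the same reference for the secondary trajectories.

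Item 1 is essential to item 3. A Kenward-Roger test from a random-intercept-only model would not correct the larger inflation in step 5 of the working; of the two options, only re-randomisation would protect against it.

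The cost is a few sentences and a little more analysis work, with no new data or design change. About 3 points of apparent power are given up (83% to 80% at the alternative in step 6), and these come only from the inflated error rate. SAP 4 says the analysis details were settled before unblinding, and this choice should be fixed on the same footing.

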Subjects recruited at Wake Forest Baptist Medical Center will be identified by research personnel in the departments of Anesthesiology and Orthopaedics. Research personnel will approach the subjects while they are in a private exam room, the study will be explained to the subject and the subject will be given a copy of the study consent form to read. Informed consent be obtained at this time or the subject may choose to take the informed consent home and call the study personnel to schedule an appointment to come to the Headache and Pain Research Unit at Piedmont Plaza 2 (HPRU) for consent and their initial study visit. Subjects will be seen in the HPRU twice; within 2 weeks prior to surgery, and approximately 2 months after surgery.

Subjects selection criteria: We will recruit patients having primary, unilateral hip arthroplasty (HA).

Inclusion criteria: Adult, non-pregnant adults scheduled for elective HA, American Society of Anesthesiologists physical status 1-3, able and willing to perform the study procedures. Individuals must be able to read and write English and have a stable residence.

Exclusion criteria: (1) inability to complete questionnaires; (2) pregnancy; (3) litigation or workers compensation related to their joint surgery; (4) taking > 100 mg morphine equivalents/day; (5) suffering from a psychotic disorder or a recent psychiatric hospitalization.

Sample size: Single-center interventional study of 120 evaluable patients having primary HA.

Interventions and interactions:

Preoperative procedures. Eligible subjects will be identified at least 2 weeks prior to surgery, informed consent obtained, and a ~ 1.5-hr preoperative assessment will be performed, consisting of 3 parts. First, we will record demographic and history information, including pre-existing pain elsewhere. Second, we will administer the 9CH iPad game. Third, we will administer questionnaire-based measures of psychological state, physical function, and pain (Table 1).

Table 1. Preoperative Questionnaire
Stanford Expectations of Therapy Scale
WOMAC- Osteoarthritis Index
Life Orientation Test-Revised (LOT-R)
PROMIS- Depression
PROMIS- Anxiety
Pain Medication Attitudes Questionnaire (PMAQ)
Pain Locus of Control Scale (PLOC)
Pain Self-Efficacy Scale (PSE)
Barratt Impulsivity Test
Fear of Pain Questionnaire
Pain Catastrophizing Scale (PCS)
Tampa Scale of Kinesiophobia (TSK)
WHO Disability Assessment (WHODAS 2.0)

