Study objective: The primary objective is to determine the effectiveness of intrathecal oxytocin to speed recovery from pain, as measured by growth curve modeling, after TKA.

Secondary objectives are:

- a. To determine the effectiveness of oxytocin to speed gain in activity, assessed by actigraphy and analyzed by growth curve modeling, after TKA
- b. To determine the effectiveness of oxytocin to speed recovery from self-assessed disability, as measured by growth curve modeling, after TKA
- c. To determine the effectiveness of oxytocin to hasten time to cessation of opioid use, as measured by growth curve modeling, after TKA

Section 3: Trial Methods

9. *Trial design*

The trial is a single center, randomized, parallel-group, placebo-controlled trial. Treatment allocation is a 1:1 ratio. Patients are randomized to either oxytocin or saline control.

10. *Randomization*

Participants were randomized into treatment arms in a 1:1 ratio using permuted blocks of sizes 4 to 8. Randomization assignments. The ‘blockrand’ package in R was used by the study statistician. Allocation concealment was maintained using a centralized pharmacy administration of study drug. Both study agents are designed to look identical to each other to maintain blinding.

11. *Sample size*

Enrolling $N = 120$ participants ($n = 60$ per study arm) provides sufficient power to examine the study’s primary hypothesis. Assuming that each individual contributes ~ 60 daily measurements, with $\alpha = 0.05$, power = .80, a modest level of within-subject correlation, and adequate model fits (SD of the residuals < 2.0), we will be able to detect difference in slopes of $d = 0.09$ units. Thus, if the saline group exhibited a mean pain score of 8.0 VAS units after surgery and decreased on average 0.38 points each day (i.e., expected full recovery at 21 days), sufficient power exists to detect an enhanced slope of 0.47 in the oxytocin group (i.e., expected full recovery in ~ 17 days). This difference is a clinically meaningful effect size that could substantially improve the life of patients.

12. *Framework*

Superiority testing will be used to examine differences between the treatment arms.

13a. *Information on interim analyses*

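### SAP item 27 gives activity and disability their own two-week preoperative baseline but not opioid self-administration, at a probable cost in precision for secondary objective c

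*SAP*

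**What the plan says.** SAP item 8 lists faster cessation of opioid use, assessed by growth curve modelling, as secondary objective c. Item 26 takes opioid self-administration from the daily diaries, days 0 to 56.

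Under items 27a/27b, the primary pain model includes "ongoing use of opioids at the time of recruitment" among the patient characteristics. It also includes daily pain and its variance over the two weeks before surgery. The trajectories for activity, disability and opioid self-administration "will be analyzed using a similar approach to that of the primary outcome, with one exception". Two exceptions follow:

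- Activity: "For the activity analysis, preoperative data covariate included will not be pain, but rather degree of daily actigraphy activity and its variance" over the two weeks before surgery.
- Disability: its own two-week level and variance, plus the baseline WHODAS 2.0 score.

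Nothing follows for opioid self-administration. The schedule in SAP item 15 marks the daily diary in the column for the 14 days before surgery. The protocol excludes patients under criterion "4) taking > 100 mg morphine equivalents/day", so lower intake is eligible. SAP item 17 says of the secondary outcomes that "each will be interpreted at the 5% level of significance with no adjustments made for multiplicity".

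**The concern.** For two of the three secondary trajectories the SAP follows a clear principle: adjust the outcome for its own level just before surgery. For the third it does not, and gives no reason. Announcing one exception and then listing two suggests that the paragraph was not checked against all three outcomes.

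Opioid use before surgery is likely to be a strong predictor of use after it. The model does carry recruitment use, but the SAP does not say whether this is a yes/no status or a dose. If it is yes/no, a patient on a small amount and one near the eligibility limit count the same. What is at stake is the precision of objective c. There is also some discretion over the covariate set, which should be closed before unblinding.

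**Working it through.** **Plan's own figures.** The only power statement concerns the primary pain outcome: "we will be able to detect difference in slopes of $d = 0.09$ units", with 60 per arm. Its recovery times check: 8/0.38 = 21.05 days and 8/0.47 = 17.02 days. A difference of 0.09 implies a per-patient slope SD of 0.09 / [(1.960 + 0.842) × √(2/60)] = 0.176, which the SAP does not state. No SD, correlation, prevalence or power is given for opioid use, so there is no opioid figure to reproduce. What follows is illustrative.

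**Step 1: how much of the preoperative amount a yes/no status captures.** Assume that a share p of patients use opioids before surgery, with amounts uniform from 5 to 100 mg/day among users. The upper end is the eligibility limit; the rest is assumed. Among users the mean is 52.5 and the variance is 95²/12 = 752.1. Then

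r² = (1 − p) × 52.5² / [(1 − p) × 52.5² + 752.1].

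For p = 0.20 this is 2205/2957.1 = 0.75.

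**Step 2: effect on the standard error.** If the preoperative amount correlates ρ with the postoperative level, replacing the status by the amount multiplies the standard error of the between-arm difference by √[(1 − ρ²)/(1 − ρ²r²)].

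| p | r² | SE reduction, ρ = 0.4 | SE reduction, ρ = 0.7 |
|---|---|---|---|
| 0.20 | 0.75 | 2.3% | 10.4% |
| 0.30 | 0.72 | 2.6% | 11.2% |
| 0.40 | 0.69 | 2.9% | 12.3% |

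Example: p = 0.40, ρ = 0.7 gives √[0.51/(1 − 0.49 × 0.687)] = √0.769 = 0.877.

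In power terms, take an effect with 80% power under the status model. It would have Φ(2.802/0.977 − 1.960) = 82% at the low end and Φ(2.802/0.877 − 1.960) = 89% at the high end.

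**Step 3: a different shape for the baseline.** Suppose instead a normal baseline, cut so that 20% to 50% are positive. The status then captures only 49% to 64% of the variance. Replacing it multiplies the residual variance by about 0.98 at ρ = 0.2, 0.86 to 0.89 at ρ = 0.5, and 0.67 to 0.74 at ρ = 0.7. Power of 80% becomes about 81%, 84–86% and 90–93%. The direction is the same. The gain at ρ = 0.7 is larger because the status carries less information.

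**Step 4: validity.** In 20,000 simulated trials of 120 patients (ρ = 0.5, 35% positive, no true effect), type I error was 5.0% with the status and 5.1% with the continuous baseline. The mean estimate was about 0.001 in both, and the standard errors were 0.168 and 0.159.

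**The case against.** The strongest reply is that the opioid model already holds a baseline for its own outcome. Recruitment use is in the common covariate set, whereas activity and disability have no such term, which may be why only those two needed a swap. Preoperative pain is also a defensible predictor of opioid use. This stands: the opioid baseline is adjusted for, if perhaps coarsely, and it would be wrong to say that the plan ignores it.

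Three further inferences are tempting, and the documents do not support them:

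- **That the diary already holds a preoperative opioid amount.** The schedule shows that a diary ran, not what it asked. The protocol's list of diary domains (Post-hospital discharge measures) omits opioids. SAP item 25a names only pain and activity as preoperative diary baselines and lists medications separately. The day 0 to 56 window in item 26 does not settle it, since the same sentence covers activity and disability, which do have preoperative values.
- **That recruitment use is measured earlier than the other baselines.** Item 15 marks medical history at both the orthopaedic clinic and V1. It places V1 2–4 weeks before surgery, while the protocol (Setting) places that visit within 2 weeks. When opioid use is recorded is not fixed.
- **That a chance imbalance in preoperative use would be mistaken for a drug effect.** Allocation is randomized 1:1 and the test level already allows for chance imbalance. Adjustment would improve accuracy in a trial that happened to be imbalanced, but its absence is not a bias.

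The size is also open to challenge. The calculation concerns level, while objective c concerns cessation through growth curves, and no gain is shown for the slope. The other covariates are left out, which would tend to shrink the gain.

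**Conclusion.** The asymmetry is on the face of item 27 and should be corrected. Its consequence is lower precision for one secondary outcome, illustratively 2% to 12% in the standard error for level. That range assumes yes/no coding, 20% to 40% users, amounts uniform from 5 to 100 mg/day and a correlation of 0.4 to 0.7. If recruitment use is entered as a dose and intake is stable up to surgery, most of the gain disappears; if intake changes before surgery, the gain grows. Type I error stays near 5%, the comparison is unbiased, and the primary analysis is untouched. The change is worth making because objective c is a named objective tested at 5% and the remedy follows the SAP's own rule.

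**What to change.** Before unblinding, make these changes:

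- **Item 27, main change.** State that for the opioid analysis the preoperative covariate will be mean daily opioid self-administration over the two weeks before surgery, from the daily diaries, provided that the preoperative diary recorded it. Keep recruitment opioid use in the model for all patients, and say how it is coded and whether preoperative pain also stays. A variance term adds little here: non-users have zero mean and zero variance, so it would largely repeat user status.
- **If the diary did not record it.** Enter recruitment opioid use as a dose where the medication history allows.
- **Missing preoperative entries.** Extend the multiple imputation of item 28 to them. Do not substitute recruitment status for a missing diary mean, which would put two different measures into one covariate.
- **Wording.** Change the single exception announced in item 27 to match those listed.

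The cost is a few sentences and one check of the diary content. If the item exists, no new data are needed.
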